4. SUBJECT DISPOSITION

4.1. Subject Enrollment and Disposition

Key study dates (i.e., first subject screened, first subject randomized, last subject randomized, last subject last visit for the primary endpoint, and last subject last visit for the CSR) will be provided.

A summary of subject enrollment will be provided by treatment group for each country, investigator within a country, and overall. The summary will present the number and percentage of subjects randomized. For each column, the denominator for the percentage calculation will be the total number of subjects analyzed for that column.

A similar enrollment table will be provided by randomization stratum. The denominator for the percentage of subjects in the stratum will be the total number of randomized subjects. If there are discrepancies in the value used for stratification assignment between the interactive web response system (IXRS) and the clinical database, the value collected in the clinical database will be used for the summary. A listing of subjects with discrepancies in the value used for stratification assignment between the IXRS and the clinical database at the time of data finalization will be provided. If there are differences between randomization stratum using screening HIV-1 RNA value and baseline HIV-1 RNA value, a listing of the differences will also be provided.

The randomization schedule used for the study will be provided as an appendix to the CSR.

A summary of subject disposition will be provided by treatment group and total based on all screened subjects. This summary will present the number of subjects screened, the number of subjects who met all eligibility criteria but were not randomized with reasons subjects not randomized, the number of subjects randomized but never dosed (if applicable), the number of subjects randomized, and the number of subjects in each of the categories listed below:

- Safety Analysis Set
- Per-Protocol Analysis Set
- Continuing study drug in the main phase
- Completed study drug in the main phase
- Did not complete study drug with reasons for premature discontinuation of study drug in the main phase (if applicable)
- Entering and treated in the extension phase
- Continuing study drug in the extension phase

- Completed study drug in the extension phase
- Did not complete study drug with reasons for premature discontinuation of study drug in the extension phase (if applicable)
- Continuing study
- Completed study
- Did not complete the study with reasons for premature discontinuation of study (if applicable)

Duration of treatment is at least 80 weeks. At Week 80, subjects in Treatment Group 4 will complete the study. Subjects in Treatment Groups 1, 2, and 3 will be given the option to receive further treatment and continue to attend visits beyond Week 80. Main phase data is defined as the data collected on/before Week 80 visit. Extension phase data is defined as the data collected after Week 80 visit.

For the status of study drug and study completion and reasons for premature discontinuation, the number and percentage of subjects in each category will be provided. The denominator for the percentage calculation will be the total number of subjects in the Safety Analysis Set corresponding to that column in that study phase (if applicable). In addition, a flowchart will be provided to depict the disposition.

The following by-subject listings will be provided by subject ID number in ascending order to support the above summary tables:

- Reasons for premature study drug or study discontinuation
- Reasons for screen failure (will be provided by screening ID number in ascending order)

4.2. Extent of Study Drug Exposure and Adherence

Study drug administration and study drug dispensing information will be collected in the Study Drug Administration and Study Drug Accountability eCRFs. All data including lot number and kit ID (if applicable) will be listed.

4.2.1. Duration of Exposure to Study Drug

Due to long acting feature of LEN, duration of follow-up to study drug will consider the prolonged exposure of LEN after the last dose date of LEN. Duration of exposure to study drug will be defined as (the last exposure date – the first dose date + 1), and will be expressed in weeks using up to 1 decimal place (eg, 4.5 weeks). Last exposure date is defined in Section 3.8.1 for subjects who prematurely discontinued study drug. For subjects who are still on study drug at the time of the data cut date of the Week 54 analysis, the data cut date will be used to impute the last exposure date.

Duration of exposure will be summarized using descriptive statistics (n, mean, SD, median, Q1, Q3, minimum, and maximum) and as the number and percentage of subjects exposed and remained through the following time periods: 1 day, 2 days, 8 days, 15 days, 4 weeks (28 days), 10 weeks (70 days), 16 weeks (112 days), 22 weeks (154 days), 28 weeks (196 days), etc. Summaries will be provided based on the Safety Analysis Set. No inferential statistics will be provided.

4.2.2. Adherence to Study Drug

4.2.2.1. Adherence to SC LEN

The adherence to SC LEN will be assessed by adherence to the projected injection interval, which is 26 weeks (182 days) between 2 adjacent injection visits. The number of days from the projected injection visit date will be calculated for each injection visit (excluding the 1st injection visit) as the injection visit date – the previous injection visit date plus 1 day minus 182 days. The number of days from the projected injection visit date will be classified into the following categories:

- < -14 days
- -14 to -8 days
- -7 to -3 days
- \pm 2 days
- 3 to 7 days
- 8 to 14 days
- > 14 days

The number and percentage of subjects in each category will be summarized for subjects in Treatment Groups 1 and 2 who receive SC injections for the injection visit of interest.

4.2.2.2. Adherence to Once Daily Study Drug(s)

The adherence to once daily (QD) study drug(s) will be calculated based on 1 study drug for Treatment Groups 1, 2, and 4 (ie, F/TAF up to Week 28 and TAF or BIC from Week 28 onwards for Treatment Groups 1 and 2, and B/F/TAF for Treatment Group 4), and 2 study drugs for Treatment Group 3 (ie, oral QD LEN and F/TAF), excluding long acting LEN used for oral lead-in.

Adherence (%) of QD study drug(s) will be calculated as follows:

$$\begin{aligned} \text{Adherence (\%)} &= 100 \times \frac{\text{Total No. of pills taken}}{\text{Total No. of pills prescribed}} \\ &= 100 \times \frac{\sum \sum \text{No. of pills taken at each dispensing period for each study drug}^{[1]}}{\sum \sum \text{No. of pills prescribed at each dispensing period for each study drug}^{[2]}} \end{aligned}$$

- [1] Number of pills taken at a distinct dispensing period for QD study drug(s) will be calculated as the minimum of (a) the daily number of pills prescribed multiplied by the duration of treatment of QD study drug(s) at the dispensing period of the same dispensing date, and (b) the number of pills taken (number of pills dispensed minus the number of pills returned). Total number of pills taken is determined by summing the number of pills taken from all evaluable dispensing periods for all QD study drug(s).
- [2] Number of pills prescribed at a distinct dispensing period for QD study drug(s) will be calculated as the daily number of pills prescribed multiplied by the duration of treatment of QD study drug(s) at the dispensing period of the same dispensing date. Total number of pills prescribed is determined by summing the number of pills prescribed from all evaluable dispensing periods for all QD study drug(s).

The duration of treatment of QD study drug(s) at a dispensing period for the study drug is calculated as the minimum of (a) the last returned date of the study drug at a dispensing period, (b) date of premature discontinuation of the study drug, and (c) next pill dispensing date of the study drug, minus dispensing date of the study drug.

The next pill dispensing date is the following dispensing date of the study drug regardless of the bottle return date.

For a record where the number of pills returned was missing (with “Yes” answered for “Was Bottle returned?” question), it is assumed the number of pills returned was zero. If the number of pills dispensed was missing or any study drug bottle was not returned or the bottle return status was unknown, all records in that dispensing period for that study drug will be excluded from both denominator and numerator calculation.

Adherence will be calculated for each subject for the entire dosing period up to the date of permanent discontinuation of the study drug for subjects who prematurely discontinued study drug or using all available data for subjects ongoing on study drug by the data cut date.

Descriptive statistics for adherence (n, mean, SD, median, Q1, Q3, minimum, and maximum) along with the number and percentage of subjects belonging to adherence categories (eg, < 80%, ≥ 80% to < 90%, ≥ 90% to < 95%, ≥ 95%) will be provided for subjects who return at least 1 bottle of randomized QD study drug, and who have calculable adherence in the Safety Analysis Set. No inferential statistics will be provided.

A by-subject listing of study drug administration and drug accountability will be provided separately by subject ID number (in ascending order) and visit (in chronological order).

4.3. Protocol Deviations

Subjects who did not meet the eligibility criteria for study entry but enrolled in the study, will be summarized regardless of whether they were exempted by the sponsor or not. The summary will present the number and percentage of subjects who did not meet at least 1 eligibility criterion and the number of subjects who did not meet specific criteria by treatment group based on the All Safety Analysis Set. A by-subject listing will be provided for those subjects who did not meet at least 1 eligibility (inclusion or exclusion) criterion. The listing will present the eligibility criterion (or criteria if more than 1 deviation) that subjects did not meet and related comments, if collected.

Protocol deviations occurring after subjects entered the study are documented during routine monitoring. The number and percentage of subjects with important protocol deviations (e.g., at least 1, with 1, 2, 3 or more important protocol deviations), and the total number of important protocol deviations by deviation category (e.g., eligibility criteria, informed consent) will be summarized by treatment group for the Safety Analysis Set. A by-subject listing will be provided for those subjects with important protocol deviation.

5. BASELINE CHARACTERISTICS

5.1. Demographics and Baseline Characteristics

Subject demographic variables (ie, age, sex at birth, gender identity, sexual orientation, race, and ethnicity) and baseline characteristics (body weight [in kg], height [in cm], body mass index [BMI; in kg/m²]) will be summarized by treatment group and overall using descriptive statistics for continuous variables and using number and percentage of subjects for categorical variables. The summary of demographic data will be provided for the Safety Analysis Set.

Statistical comparison across treatment groups will be performed. For categorical data, the Cochran-Mantel-Haenszel (CMH) test will be used to compare across treatment groups except for gender identity and sexual orientation. For continuous data, the 2-sided Kruskal-Wallis test will be used to compare across treatment groups.

A by-subject demographic listing, including the informed consent date, will be provided by subject ID number in ascending order.

5.2. Other Baseline Characteristics

The following baseline disease characteristics will be summarized by treatment group and overall using descriptive statistics for continuous variables and using number and percentage of subjects for categorical variables:

- HIV-1 RNA (log₁₀ copies/mL)
- HIV-1 RNA categories (copies/mL): (a) ≤ 100,000, (b) > 100,000
- CD4 cell counts (/uL)
- CD4 cell counts categories (/uL): (a) < 50, (b) ≥ 50 to < 200, (c) ≥ 200 to < 350, (d) ≥ 350 to < 500, and (e) ≥ 500
- CD4 percentage (%)

The summary of these baseline disease characteristics will be provided for the Safety Analysis Set. Statistical comparison across treatment groups will be conducted similarly as described for the demographic and baseline characteristics.

A by-subject listing of other baseline characteristics will be provided by subject ID number in ascending order.

5.3. Medical History

General medical history data will be collected at screening including HIV-1 disease-related events. General medical history data will be coded and listed.

6. EFFICACY ANALYSES

6.1. Primary Efficacy Endpoint

The primary efficacy endpoint is the proportion of subjects with HIV-1 RNA < 50 copies/mL at Week 54 as determined by the United States (US) Food and Drug Administration (FDA)-defined snapshot algorithm {[U. S. Department of Health and Human Services 2015](#)}. The proportions are expressed as percentages for presentation purposes.

6.1.1. US FDA-defined Snapshot Algorithm

The analysis window at Week 54 is defined as from Study Day 323 to Study Day 413, inclusive. All HIV-1 RNA data collected on-treatment (ie, data collected up to 1 day after the last dose date) will be used in the US FDA-defined snapshot algorithm. Virologic outcome will be defined as the following categories:

- HIV-1 RNA < 50 copies/mL: this includes subjects who have the last available on-treatment HIV-1 RNA < 50 copies/mL in the Week 54 analysis window
- HIV-1 RNA \geq 50 copies/mL: this includes subjects
 - Who have the last available on-treatment HIV-1 RNA \geq 50 copies/mL in the Week 54 analysis window, or
 - Who do not have on-treatment HIV-1 RNA data in the Week 54 analysis window and
 - Who discontinue study drug prior to or in the Week 54 analysis window due to lack of efficacy, or
 - Who discontinue study drug prior to or in the Week 54 analysis window due to reasons other than AE, death, or lack of efficacy and have the last available on-treatment HIV-1 RNA \geq 50 copies/mL
- No Virologic Data in the Week 54 analysis window: this includes subjects who do not have on-treatment HIV-1 RNA data in the Week 54 analysis window because of the following:
 - Discontinuation of study drug prior to or in the Week 54 analysis window due to AE or death (regardless of whether the last available on-treatment HIV-1 RNA < 50 copies/mL or not) or,
 - Discontinuation of study drug prior to or in the Week 54 analysis window due to reasons other than AE, death, or lack of efficacy and the last available on-treatment HIV-1 RNA < 50 copies/mL or,
 - Missing data during the window but on study drug.

The flowchart of the US FDA-defined snapshot algorithm is provided in Section 12 ([Appendix 2](#)).

6.1.2. Primary Analysis of the Primary Efficacy Endpoint

The proportion of subjects with HIV-1 RNA < 50 copies/mL as determined by the US FDA-defined snapshot algorithm at Week 54 will be based on the FAS. Point estimates ($P_1 - P_2$) and its 95% confidence interval (CI) for the difference in the response rates between each of the LEN-containing regimen groups (Treatment Groups 1 to 3) and the B/F/TAF group (Treatment Group 4) will be constructed using stratum-adjusted Mantel-Haenszel (MH) proportion as described as follows {Koch 1989}, stratified by baseline HIV-1 RNA level ($\leq 100,000$ copies/mL or $> 100,000$ copies/mL):

$$P_1 - P_2 \pm Z_{(1-\alpha/2)} * SE(P_1 - P_2),$$

where

- $(P_1 - P_2) = \frac{\sum w_h d_h}{\sum w_h}$, is the stratum-adjusted MH proportion difference,

where $d_h = p_{1h} - p_{2h}$ is the difference in the response rate between of the LEN-containing regimen groups (Treatment Groups 1 to 3) and the B/F/TAF group (Treatment Group 4) in stratum h ($h=1$ to 4).

- $w_h = \frac{n_{1h} n_{2h}}{n_{1h} + n_{2h}}$, is the weight based on the harmonic mean of sample size per treatment group for each stratum where n_{1h} and n_{2h} are the sample sizes of the LEN-containing regimen groups (Treatment Groups 1 to 3) and the B/F/TAF group (Treatment Group 4) in stratum h .

- $SE(P_1 - P_2) = \sqrt{\frac{\sum w_h^2 \left[\frac{p_{1h}^* (1 - p_{1h}^*)}{n_{1h} - 1} + \frac{p_{2h}^* (1 - p_{2h}^*)}{n_{2h} - 1} \right]}{(\sum w_h)^2}}$, where $p_{1h}^* = \frac{m_{1h} + 0.5}{n_{1h} + 1}$ and

$p_{2h}^* = \frac{m_{2h} + 0.5}{n_{2h} + 1}$. m_{1h} and m_{2h} are the number of subjects with HIV-1 RNA < 50 copies/mL in the LEN-containing regimen groups (Treatment Groups 1 to 3) and the B/F/TAF group (Treatment Group 4) in stratum h .

- $\alpha = 0.05$ for this study
- $Z_{(1-\alpha/2)} = Z_{0.9750} = 1.96$ is the 97.50th percentile of the normal distribution

Note that if the computed lower confidence bound is less than -1 , the lower bound is defined as -1 . If the computed upper confidence bound is greater than 1 , the upper bound is defined as 1 .

The number and percentage of subjects with HIV-1 RNA < 50 copies/mL at Week 54 will be summarized. The associated p-values will be estimated based on the CMH test stratified by baseline HIV-1 RNA level ($\leq 100,000$ copies/mL or $> 100,000$ copies/mL).

6.1.3. Secondary Analysis for the Primary Efficacy Endpoint

A secondary analysis based on the Week 54 PP analysis set will also be performed to evaluate the robustness of the primary analysis of the primary endpoint. Subjects excluded from the Week 54 PP analysis set will be determined before database lock.

6.2. Secondary Efficacy Endpoints

The secondary efficacy endpoints of this study are:

- The proportion of subjects with HIV-1 RNA < 50 copies/mL at Weeks 28, 38, and 80 as determined by the US FDA-defined snapshot algorithm
- The change from baseline in \log_{10} HIV-1 RNA and in CD4+ cell count at Weeks 28, 38, 54, and 80

The proportion of subjects with HIV-1 RNA < 50 copies/mL at Week 28 as determined by the US FDA-defined snapshot algorithm has been performed in the Week 28 analyses and will not be repeated here. The proportion of subjects with HIV-1 RNA < 50 copies/mL at Week 38 as determined by the US FDA-defined snapshot algorithm will be analyzed using the same method as the primary analysis for the primary endpoint based on the FAS.

The proportion of subjects with HIV-1 RNA < 50 copies/mL as determined by the US FDA-defined snapshot algorithm at Week 80 will not be summarized for the Week 54 interim analysis as the majority of subjects will not have reached the timepoints of interest.

6.2.1. Analysis of the Secondary Efficacy Endpoints

The change from baseline in \log_{10} HIV-1 RNA and in CD4+ cell counts will be based on the FAS and summarized up to the visits with available data using descriptive statistics. The differences in changes from baseline in \log_{10} HIV-1 RNA and CD4+ cell count between each of the LEN-containing treatment groups (Treatment Groups 1-3) and the B/F/TAF group (Treatment Group 4) and the associated p-values and 95% CIs will be constructed using analysis of variance (ANOVA) models adjusting for the baseline HIV-1 RNA level ($\leq 100,000$ copies/mL or $> 100,000$ copies/mL).

Mean \pm 95% CI and median (Q1, Q3) of the change from baseline in \log_{10} HIV-1 RNA and CD4+ cell counts will be plotted by visit.

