Participants in Group 1 and Group 2 may require oral weekly bridging 300 mg if a SC injection of GS-6207 cannot be administered for any reason within the protocol visit window.

**Reference Therapy,
Dose, and Mode of
Administration:**

Treatment Group 4

Oral B/F/TAF

None after Week 80

**Criteria for
Evaluation:**

- Safety:** Incidence of treatment-emergent adverse events (TEAEs) and treatment-emergent clinical laboratory abnormalities
- Efficacy:** The primary endpoint of this study is:
- The proportion of participants with HIV-1 RNA < 50 copies/mL at Week 54 as determined by the Food and Drug Administration (FDA)-defined snapshot algorithm
- The secondary endpoints of this study are:
- The proportion of participants with HIV-1 RNA < 50 copies/mL at Weeks 28, 38, and 80 as determined by the FDA-defined snapshot algorithm
 - The change from baseline in \log_{10} HIV-1 RNA and in CD4+ cell count at Weeks 28, 38, 54, and 80
- Pharmacokinetics:** The following PK parameters will be calculated for GS-6207, TAF, and BIC (and metabolites, as appropriate) in plasma, as appropriate.
CCI
AUC_{0-t}, AUC_{tau}, AUC_{last}, CL/F, t_{1/2}, λ_z , V_z/F, C_{max}, T_{max}, C_{last}, T_{last}, C_{tau}, C_t
- Statistical Methods:** The primary efficacy analysis is to compare the proportion of participants with HIV-1 RNA < 50 copies/mL at Week 54 as determined by the US FDA-defined snapshot algorithm. Point estimates and 95% confidence interval (CI) for the difference in the response rates between each of the GS-6207-containing regimen groups (Treatment Groups 1 to 3) and the B/F/TAF group (Treatment Group 4) will be constructed using normal approximation method, stratified by baseline HIV-1 RNA level ($\leq 100,000$ copies/mL or $> 100,000$ copies/mL). The percentage of participants with HIV-1 RNA < 50 copies/mL at Weeks 28, 38, and 80 respectively, as determined by the US FDA-defined snapshot algorithm will be analyzed using the same methods as for the primary efficacy endpoint. Baseline HIV-1 RNA level ($\leq 100,000$ copies/mL or $> 100,000$ copies/mL) adjusted differences in change from baseline in \log_{10} HIV-1 RNA and CD4+ cell count at Weeks 28, 38, 54, and 80 between each of the GS-6207-containing regimen groups (Treatment Groups 1 to 3) and the B/F/TAF group (Treatment Groups 4) and the associated

95% CIs will be constructed using analysis of variance (ANOVA) models.

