8.5.2. Secondary Analyses

The proportion of participants with HIV-1 RNA < 50 copies/mL at Weeks 28, 38, and 80, respectively, will be analyzed using the same methods as for the primary efficacy endpoint.

The changes from baseline in \log_{10} HIV-1 RNA and CD4+ cell count will be summarized using descriptive statistics. The differences in changes from baseline in \log_{10} HIV-1 RNA and CD4+ cell count between treatment groups and the associated 95% CIs will be constructed using analysis of variance (ANOVA) models adjusting for the baseline HIV-1 RNA level.

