3.3. Strata and Covariates

Randomization was stratified by HIV-1 RNA level ($\leq 100,000$ copies/mL or $> 100,000$ copies/mL) at screening.

Efficacy analyses will include HIV-1 RNA stratum ($\leq 100,000$ vs. $> 100,000$ copies/mL) at baseline as a stratification factor. The HIV-1 RNA stratum will be reclassified using baseline HIV-1 RNA level for analysis purposes.

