Logarithmic (base 10) transformations will be applied to HIV-1 RNA data for efficacy analysis. HIV-1 RNA results of ‘No HIV-1 RNA detected’ and “<20 cp/mL HIV-1 RNA Detected” will be imputed as 19 copies/mL for analysis purposes.

Natural logarithm transformation will be used for analyzing concentrations and PK parameters in intensive PK samples. Concentration values that are BLQ will be presented as “BLQ” in the concentration data listing. Values that are BLQ will be treated as 0 at predose time points, and one-half the value of the LOQ at postdose time points for summary purposes.

The following conventions will be used for the presentation of summary and order statistics for intensive PK concentrations:

- If at least 1 subject has a concentration value of BLQ for the time point, the minimum value will be displayed as “BLQ.”
- If more than 25% of the subjects have a concentration data value of BLQ for a given time point, the minimum and Q1 values will be displayed as “BLQ.”
- If more than 50% of the subjects have a concentration data value of BLQ for a given time point, the minimum, Q1, and median values will be displayed as “BLQ.”
- If more than 75% of the subjects have a concentration data value of BLQ for a given time point, the minimum, Q1, median, and Q3 values will be displayed as “BLQ.”
- If all subjects have concentration data values of BLQ for a given time point, all order statistics (minimum, Q1, median, Q3, and maximum) will be displayed as “BLQ.”

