6.5. Changes from Protocol-Specified Efficacy Analyses

No change from protocol-specified efficacy analysis is planned.

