$$\begin{aligned} \text{Adherence(\%)} &= 100 \times \frac{\text{Total No. of pills taken}}{\text{Total No. of pills prescribed}} \\ &= 100 \times \frac{\sum \sum \text{No. of pills taken at each dispensing period for each drug}^{[1]}}{\sum \sum \text{No. of pills prescribed at each dispensing period for each drug}^{[2]}} \end{aligned}$$

13) Efficacy Analysis

- a) For categorical efficacy response (eg, Subjects with HIV-1 RNA < 50 copies/mL as determined by US FDA-defined snapshot algorithm, M=F, or M=E Analyses): the proportion difference between LEN-containing regimen groups (Treatment Groups 1 to 3) and the B/F/TAF group (Treatment Group 4) and its 95% CIs are calculated based on the MH proportion adjusted by baseline HIV-1 RNA stratum ($\leq 100,000$ vs. $> 100,000$ copies/mL) (see SAP Section 6.2 and 6.3 for details). The following SAS code will be used to compute p-value, where *brnac* is the baseline HIV-1 RNA stratum, *trtgrp* is the treatment, and *response* is the categorical efficacy response.

```
proc freq data=adeff;  
  tables brnac*trtgrp*response/cmh; /*p value from general  
  association*/  
run;
```

- b) All the ANOVA model for continuous efficacy variable (eg, CD4+): The differences in changes from baseline in \log_{10} HIV-1 RNA and CD4+ cell count between treatment groups and the associated 95% CI will be constructed using an ANOVA, including baseline HIV-1 RNA stratum *brnac*, region stratum *region*, and treatment *trtgrp* as fixed effects in the model.

```
proc glm data=adeff;  
  class brnac region trtgrp;  
  model CD4=brnac region trtgrp;  
  lsmeans trtgrp /alpha=0.05 cl pdiff;  
run;
```

14) Listing for US FDA-defined snapshot outcome:

In addition flag the values of HIV-1 RNA < 50 or ≥ 50 copies/mL for virologic outcomes.

Flag the last available HIV-1 RNA value while on treatment for the following categories:

- a) HIV-1 RNA ≥ 50 copies/mL - Discontinued Study Drug Due to Other Reasons and Last Available HIV-1 RNA ≥ 50 copies/mL
- b) No virologic Data - Discontinued Study Drug Due to Other Reasons and Last Available HIV-1 RNA < 50 copies/mL

15) Injection site reaction (ISR)

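### Change in log10 HIV-1 RNA is adjusted for baseline only in two classes, which costs precision, and the programmed model adds a region term that the SAP text and protocol do not name

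*SAP*

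**What the plan says.** SAP 6.2.1 compares each lenacapavir group with B/F/TAF on change in log10 HIV-1 RNA and in CD4+ count. Differences, p-values and 95% intervals "will be constructed using analysis of variance (ANOVA) models adjusting for the baseline HIV-1 RNA level", in two classes cut at 100,000 copies/mL. The protocol synopsis gives the same two classes for the "adjusted differences in change from baseline in" both variables. Protocol 8.5.2 specifies "analysis of variance (ANOVA) models adjusting for the baseline HIV-1 RNA level" without saying whether that level is a class or a number.

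The continuous value exists. SAP 3.8.1 defines baseline as the last value up to first dose, SAP 3.7 log-transforms HIV-1 RNA, and SAP 5.2 summarises the baseline on the log10 scale. SAP 3.7 also sets a floor: undetected results and those below 20 copies/mL "will be imputed as 19 copies/mL for analysis purposes".

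Appendix 3 item 13(b) gives a different model. Its text adds a region stratum as a fixed effect, and its code reads "model CD4=brnac region trtgrp". SAP 3.3 names one factor only: "Randomization was stratified by HIV-1 RNA level". SAP 6.5 states: "No change from protocol-specified efficacy analysis is planned".

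**The concern.** There are two separate points.

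**Precision.** When nearly everyone is suppressed and recorded at 19 copies/mL (log10 = 1.28), change is approximately 1.28 minus baseline. Most of its variance is then baseline variance. A two-class term removes part of this and leaves the rest in the residual. With about 25 controls, chance baseline differences within a class pass into the estimated treatment difference. Protocol 1.2.2.8 reads the absence of a significant difference on this endpoint as similar results across groups, and that reading is easier to reach with a wider interval.

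**Specification.** The SAP text and the SAP code describe different models for the same endpoint. Region has no defined levels and was not a randomisation factor. A programmer following Appendix 3 and a reader following SAP 6.2.1 would expect different analyses.

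**Working it through.** **The plan's own figure.** The documents give no precision target for this endpoint. The one design figure, 39% power for non-inferiority on the Week 54 response rate, reproduces: Φ(0.12/√(0.909 × 0.091 × (1/50 + 1/25)) − 1.96) = 39.9%. Nothing below affects it.

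**Inputs (Protocol 1.2.2.8).** Baseline log10 HIV-1 RNA: median 4.37, quartiles 3.86 and 4.74. At or below 100,000 copies/mL: 155 of 182, so 27 above. SD of Week 54 change, Groups 1 to 4: 0.636, 0.589, 0.840, 0.787.

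**Baseline SD, assuming normality.** From the quartiles: (4.74 − 3.86)/1.349 = 0.652. From the share above the cut: (5 − 4.37)/z(1 − 27/182) = 0.63/1.044 = 0.604. An SD of 0.50 is added as a low case that does not come from the documents.

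**Share of baseline variance captured by two classes.** R² = φ(z)²/(q(1 − q)) with q = 27/182, which gives 0.424. It is 0.35 at SD 0.50 and 0.45 at SD 0.652.

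**Pooled SD of Week 54 change.** Weights are n − 1 with n = 52, 53, 52, 25 (full analysis set sizes, assumed to be the numbers observed): √0.503 = 0.709.

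**Closed form.** Let Vb be the baseline variance and Vc the variance of change. If the follow-up value is independent of baseline, the ratio of planned SE to SE with continuous baseline is √(1 + Vb(1 − R²)/(Vc − Vb)). At SD 0.50, for example, √(1 + 0.25 × 0.65/0.253) = 1.28.

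**Simulation.** There were 4,000 trials per setting with 50/50/50/25 participants, allocation balanced within stratum, a four-arm fit and no true effect. Suppressed values were 85% at 19 copies/mL and 15% at 20 to 49 (assumed). Unsuppressed values were log-uniform from 50 up to the smaller of own baseline and 100,000 (assumed). The unsuppressed share was tuned to an SD of change of 0.709.

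| Baseline SD | Unsuppressed | Closed-form ratio | Planned SE | SE with continuous baseline | Ratio by sampling SD |
|---|---|---|---|---|---|
| 0.50 | 7.9% | 1.28 | 0.159 | 0.127 | 1.2 |
| 0.55 | 6.2% | 1.39 | 0.153 | 0.113 | 1.3 |
| 0.60 | 4.3% | 1.58 | 0.146 | 0.095 | 1.5 |
| 0.65 | 2.3% | 2.00 | 0.137 | 0.070 | 1.9 |

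Multiplying by 1.96, the 95% half-width in log10 copies/mL falls from 0.31 to 0.25 (SD 0.50), from 0.29 to 0.19 (0.60) and from 0.27 to 0.14 (0.65). Mean estimates were within 0.003 of zero in both models. Coverage was 94.4–95.7% for the plan and 95.2–96.3% with continuous baseline.

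The planned estimate correlated −0.60 to −0.84 with the baseline difference between arms (−0.48 to −0.64 under simple allocation), against about 0 after continuous adjustment.

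**By comparison.** The closed form with pairwise pooled SDs at SD 0.50/0.60/0.65 gives 1.2/1.3/1.4 for Group 3 v 4 and 1.3/1.7/2.4 for Group 1 v 4. For Group 2 v 4 it gives 1.4/2.0/unstable, because that arm's SD of change (0.589) is below both document-based baseline SDs. At Week 38 (pooled SD 0.697) the four-arm ratios are 1.3, 1.6 and 2.2.

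**CD4.** The documents do not give the correlation between baseline and change. If it is between 0 and 0.5, the planned interval is wider by a factor 1/√(1 − r²), which is 1.00 to 1.15.

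**Region.** Set side by side, Appendix 3 item 13(b) has HIV-1 RNA class, region and treatment. SAP 6.2.1 and Protocol 8.5.2 have HIV-1 RNA and treatment, and SAP 3.3 lists HIV-1 RNA class as the only stratification factor. In the simulation at SD 0.60, a region term unrelated to outcome left the planned SE at 0.146. SAP 6.1.2 also indexes four strata where its only stratifier has two classes. That would fit text carried over from a design stratified by region as well, but this is inference.

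**The case against.** The strongest reply is that the first point identifies no error. The two-class model was prespecified, uses the classes of the randomisation variable, and is unbiased with correct coverage. SAP section 3 calls the tests descriptive, SAP 3.5 calls the trial non-confirmatory, and no margin or decision rule applies here. All of that stands, and it limits the point to precision.

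The size can also be questioned. Normality is assumed, and the quartiles are asymmetric: 0.51 below the median and 0.37 above, or SDs of about 0.76 and 0.55 when each is divided by 0.6745. The upper-half value lies within the range shown. At 0.76 the closed form has no solution, since Vb would exceed Vc. Ratios by sampling SD are slightly lower than the model-based ones. In a separate two-arm simulation with only 1% unsuppressed, the continuous model's reported SE was too small (0.046 against a sampling SD of 0.055). So the direction is firm and the exact ratio is not.

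Once baseline is removed, the contrast mostly reflects who is off the floor, which the primary endpoint and the missing-equals-failure and missing-equals-excluded tables already show. That limits the practical value of the gain.

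The synopsis fixes the two-class model through Week 80, so changing it must be declared, and the Week 80 SAP is not available to check.

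On region, the SAP is based on protocol amendment 3, whereas the protocol supplied is later because it reports Week 54 results. The conflict with SAP 6.5 is therefore shown only against the supplied protocol. The conflict within the SAP does not depend on the version.

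**Conclusion.** Both points hold, at the level of an improvement to consider. For HIV-1 RNA the planned SE is about 1.3 to 2.0 times what the collected baseline would allow at Week 54, or 1.2 to 1.9 by sampling SD. It varies by comparison, with the smallest loss for Group 3 v 4. This assumes a normal baseline with SD 0.50 to 0.65, follow-up values unrelated or only weakly related to baseline, and observed numbers equal to the full analysis set. Without calibration to the reported SDs, over the same range of baseline SD and an assumed 1–10% unsuppressed, the ratio runs from 1.2 to 2.7. No bias is involved and no loss is shown for CD4.

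The region term is a plain inconsistency in the SAP. Its numerical effect is negligible if region is unrelated to outcome, but the model is not uniquely specified.

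**What to change.** **HIV-1 RNA.** For Week 80, specify in advance a model with treatment, HIV-1 RNA stratum and continuous baseline log10 HIV-1 RNA, and declare it as a change from the protocol. For Weeks 28, 38 and 54, which are already reported, give the same model only as a supportive re-analysis. Adding baseline CD4 to the CD4 model is optional.

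**Region.** Remove it from Appendix 3 item 13(b), or define its levels, add it to SAP 6.2.1 and declare it in SAP 6.5, so that these sections and the protocol agree.

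**Cost.** One covariate and its declaration for Week 80, one supportive table for the earlier weeks, and a wording or code correction. No new data are needed. The present SAP covers Week 54 only, so the Week 80 change belongs in the SAP for that analysis.
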